
confirm that the participant is eligible and appropriate for the study. After participants complete the screening procedures described above, provide their informed consent to participate, and are enrolled into the study, they will complete four study assessment visits over 24 months. The first visit or baseline visit (Month 0) will occur within approximately 2-8 weeks of bariatric surgery. Subsequent visits will occur at 6, 12, and 24 months follow-up. Follow-up assessments will occur within an approximate 8week window that includes 4 weeks on either side of the target date. The procedures to be completed in preparation for each of these visits are described below. Throughout participation in the study, participants medical records will be reviewed and data will be collected to obtain psychological diagnoses (including any psychiatric medications the participant is taking), appointment dates for the bariatric surgery program (to track progress through to surgery), and date and type of bariatric surgery. Assessment Visits Participants will complete the following assessments at baseline, and 6, 12, and 24 months after surgery. Participants whose surgery date is scheduled greater than 90 days after their baseline assessment (due to delays in scheduling surgery) may be asked to return to the clinic to complete a portion of the assessment. Participants will be asked to complete the ASA 24 hour dietary food recall and the impulsivity tasks (described above) within approximately 2-8 weeks prior to surgery in order to ensure that these data are within the appropriate time frame prior to surgery. We anticipate that this portion of this assessment will take approximately one hour to complete. If participants are willing to return to the clinic to complete these two portions of the assessment, they will be compensated \$25 for their time. Prevalence and Control of Chronic Diseases: 1) T2D will be identified using hemoglobin A1c (HbA1c) and glucose measurements obtained from fasting blood samples, and will be defined as HbA1c 6.5% and glucose 7.0 mmol/L (126 mg/dL), or use of antidiabetes medication.36 Prevalence will be calculated using number of participants with T2D as the numerator and total number of participants as the denominator. Controlled T2D, among individuals diagnosed with T2D, will be defined as HbA1c 7.0%.36 These labs are drawn as part of standard clinical care and the HbA1c and glucose results will be extracted from the EMR of enrolled participants. Participants will not be asked to have additional blood draws as part of the study. 2) Hypertension: systolic blood pressure (SBP) and diastolic blood pressure (DBP) will be measured using a Dinamap 9300XL monitor.. Using recently updated US guidelines, hypertension will be defined as SBP130 mm Hg, or DBP80 mm Hg, or use of antihypertensive medication.39 Prevalence will be calculated using number of participants with hypertension as the numerator and total number of participants as the denominator. Controlled hypertension, among individuals with hypertension, will be defined as SBP130 mm Hg and DBP80 mm Hg.39 Blood pressure is measured as part of standard clinical care. SBP and DBP will also be extracted from the medical record of enrolled participants from their preoperative testing with the bariatric surgery program as well as their postoperative follow up with the surgical team. Healthcare Utilization: This information will be extracted from electronic medical records (EMRs) for the following services: primary care, hospitalizations, and emergency room visits. Total number of visits and number of visits to each service will be calculated for all-cause, mental health, T2D, and hypertension related, separately. Duration of stay will also be assessed.41,42 Based on previous experience of the research team, over 70% of participants will receive their non-bariatric care in the TU or Penn systems during the study. Therefore, we will be able to obtain utilization records through the EMR.

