psychosocial status in the first two years after bariatric surgery. Secondary outcomes will include prevalence and control of Type 2 diabetes (T2D) and hypertension, health services utilization, and adherence to antidiabetes and antihypertensive medication. Participants will be 300 adults who plan to undergo bariatric surgery. Participants will complete four assessments over a two-year period, one at baseline (before surgery) and 6, 12, and 24 months after surgery. Each assessment will include computer tasks, surveys, clinical interview, urine test, waist circumference and height/weight measurement. We will track how psychopathology, disordered eating, and impulsivity are related to changes in weight, psychosocial status, and secondary outcomes listed above, following bariatric surgery.

Objectives

Overall objectives

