Individuals interested in bariatric surgery at Penn rst attend an information session at which they are provided an overview of the program. These sessions are led by [name], Co-Investigator and Director of the Bariatric Surgery Program, or one of his surgeon colleagues. Those who desire to have surgery schedule an initial consultation with a bariatric surgeon who evaluates their medical appropriateness for surgery. As recommended by the ASMBS and required by third party payers in the region, patients also undergo a psychosocial evaluation which evaluates their psychological appropriateness for surgery and identies behavioral issues that may impact their postoperative outcome. In our program, patients attend 3 to 6 monthly, preoperative weight management (MWM) sessions (the exact number is dictated by each patients insurer). Patients will meet with the research coordinator (RC) approximately 8-10 weeks before surgery at one of their MWM visits, who will introduce the study and describe its goals and requirements. Similarly, at the Temple Health Bariatric Surgery Program, participants will be introduced to the study by the RC at their pre-operative nutrition class or one of their MWM sessions. The population of Spanish-speaking patients at Temple Health is higher than that of Penns program. At Temple Health only, we will provide participants with the option of participation in the study using Spanish language forms. A Spanish consent form will be provided and these will be reviewed by a Spanish speaking Research Coordinator. All other research procedures described below will be the same as those at already approved at Penn and Temple. If patients express interest in participation, the RC will conduct a brief screen to assess eligibility. At this screening visit, candidates will meet individually with the research coordinator, who will explain the study and obtain participants informed consent. Medical history and physical information as well as the Beck Depression Inventory II, The Weight and Lifestyle Inventory, height, weight will be reviewed from the Bariatric Surgery Program. If patients meet the inclusion criteria, they will give their written informed consent to participate and will be scheduled for baseline assessments (described below) which will be coordinated with their next preoperative weight management session, if possible. Prior to this session, the RC will review the patients medical records and meet with the Principal Investigator and research team to conrm that the participant is eligible and appropriate for the study. After participants complete the screening procedures described above, provide their informed consent to participate, and are enrolled into the study, they will complete four study assessment visits over 24 months. The first visit or baseline visit (Month 0) will occur within approximately 2-8 weeks of bariatric surgery. Subsequent visits will occur at 6, 12, and 24 months follow-up. Follow-up assessments will occur within an approximate 8-week window that includes 4 weeks on either side of the target date. The procedures to be completed in preparation for each of these visits are described below. Throughout participation in the study, participants medical records will be reviewed and data will be collected to obtain psychological diagnoses (including any psychiatric medications the participant is taking), appointment dates for the bariatric surgery program (to track progress through to surgery), and date and type of bariatric surgery.

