
Will the recruitment plan propose to use any Penn media services (communications, marketing, etc.) for outreach via social media avenues (examples include: Facebook, Twitter, blogging, texting, etc.) or does the study team plan to directly use social media to recruit for the research?

The following documents are currently attached to this item:

There are no documents attached for this item.

Subject compensation*

Will subjects be financially compensated for their participation? Yes

The following documents are currently attached to this item:

There are no documents attached for this item.

If there is subject compensation, provide the schedule for compensation per study visit or session and total amount for entire participation, either as text or separate document

Participants will receive \$100 for the baseline assessment and \$50 of participant payments for the 6and 12- month visits, and \$100 for the 24-month visit, for a total of \$300 over the course of the study. Participants will also receive compensation for parking/travel. Each visit lasts approximately 4 hours. If participants do not complete all study visits, they will receive compensation based on the number of visits completed. Participants will receive an additional \$25.00 gift card if they are requested to return for repeat measures.

Study Procedures

Suicidal Ideation and Behavior

Does this research qualify as a clinical investigation that will utilize a test article (ie- drug or biological) which may carry a potential for central nervous system (CNS) effect(s)? No

Procedures

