eligibility criteria and ethnic diversity goals outlined in the grant proposal. Once participants have completed a baseline assessment, data on compliance to the protocol will be collected by research staff and reviewed by the study investigators, the study biostatistician, and the safety officer ([name], Department of Endocrinology and associated faculty at the Center for Weight and Eating Disorders at the Perelman School of Medicine at the University of Pennsylvania). Compliance will be reviewed with the semi-annual DSMP report (described below) and if the safety officer has concerns about whether compliance has reached a level that might inhibit the ability of the study to test its primary hypotheses, he/she will suggest a conference call for study investigators to discuss methods for improving compliance. In addition, the bariatric surgeons will inform the research team of any surgical or medical complications that occurred peri- or post-operatively among surgery patients. The research coordinator will file all meeting agenda and reports in the study regulatory binder. Assessing Adverse Events Definitions Unanticipated Problems Involving Risk to Subjects or Others Any incident, experience, or outcome that meets all of the following criteria: Unexpected in nature, severity, or frequency (i.e. not described in study-related documents such as the IRB-approved protocol or consent form, the investigators brochure, etc) Related or possibly related to participation in the research (i.e. possibly related means there is a reasonable possibility that the incident experience, or outcome may have been caused by the procedures involved in the research) Suggests that the research places subjects or others at greater risk of harm (including physical, psychological, economic, or social harm). Adverse Event An adverse event (AE) is any symptom, sign, illness or experience that develops or worsens in severity during the course of the study. Intercurrent illnesses or injuries should be regarded as adverse events. Abnormal results of diagnostic procedures are considered to be adverse events if the abnormality: results in study withdrawal is associated with a serious adverse event is associated with clinical signs or symptoms leads to additional treatment or to further diagnostic tests is considered by the investigator to be of clinical significance Serious Adverse Event Adverse events are classified as serious or non-serious. A serious adverse event is any AE that is: fatal life-threatening requires or prolongs hospital stay (not including expected hospitalizations related to bariatric surgery) results in persistent or significant disability or incapacity a congenital anomaly or birth defect an important medical event Important medical events are those that may not be immediately life threatening, but are clearly of major clinical significance. They may jeopardize the subject, and may require intervention to prevent one of the other serious outcomes noted above. For example, drug overdose or abuse, a seizure that did not result in in-patient hospitalization, or intensive treatment of bronchospasm in an emergency department would typically be considered serious. All adverse events that do not meet any of the criteria for serious should be regarded as non-serious adverse events. Adverse Event Reporting Period The study period during which adverse events must be reported is normally defined as the period from the initiation of any study procedures to the end of the study treatment follow-up. For this study, the study treatment follow-up is defined as at the 18month study assessment visit. Preexisting Condition A preexisting condition is one that is present at the start of the study. A preexisting condition should be recorded as an adverse event if the frequency, intensity, or the character of the condition worsens during the study period. General Physical Examination Findings At screening and baseline visits, any clinically significant abnormality should be recorded as a preexisting condition. At the end of the study, any new clinically significant findings/abnormalities that meet the definition of an adverse event will be recorded and documented as an adverse event. Abnormal Laboratory Values A clinical laboratory abnormality should be documented as an adverse event if any one of the following conditions is met: The laboratory abnormality is not otherwise refuted by a repeat test to confirm the abnormality The abnormality suggests a disease and/or organ toxicity The abnormality is of a degree that requires active management; e.g. change of dose, discontinuation of the drug, more frequent follow-up assessments, further diagnostic investigation, etc. Expected events Over the 24-month duration of the study, a number of medical events may be expected to occur in obese adults, including routine surgeries and procedures, the development of cancer or chronic conditions, new or increased symptoms from a chronic condition, musculoskeletal problems, and motor vehicle or other accidents (e.g., falls). We will record unexpected events which occur as a result of participation in this research study. The events will be reported to the DSMP but not the IRB. Monitoring for Adverse Events (AEs) and Serious Adverse Events SAEs) Surveillance for SAEs and other relevant clinical events that may be associated with study participation will occur at 6, 12, and 24 months. This will be done using an open-ended questionnaire which asks about new symptoms, urgent/unplanned medical care, and hospitalizations. All adverse events will be recorded but only related, unexpected, and serious events will be reported. Monitoring and Reporting: will be conducted in real-time by all study personnel who have direct contact with participants. Participants will also be instructed to contact the study physician, [name], should they experience any adverse events that occur due to participation to the research between study visits. Drs. [name] and [name] will review all the Adverse and Unexpected Event Case Report Forms. After removing identifying patient health information, any AE that is related AND unexpected will be reported to the University of Pennsylvania Institutional Review Board within 10 days. Serious adverse events (e.g., unexpected hospitalization see definition above) will be brought to the attention of the Investigators and study physician within 24 hours and reported in a timely fashion as required by the Data and Safety Monitoring Plan (DSMP), the IRB, and the NIH. If the serious adverse event involved a death that is unforeseen (unexpected) and indicates participants or others are at increased risk of harm, it will be reported to the IRB within 24 hours. For all other deaths the investigators will submit a report to the IRB within 3 days. Data, safety and monitoring report. The PIs will provide a summary of the DSMP report to the NIH on an annual basis, as part of the progress report. The DSMP report will include the participants sociodemographic characteristics, expected versus actual recruitment rates, retention rates, any quality assurance or regulatory issues that occurred during the past year, summaries of AEs and SAEs, and any actions or changes with respect to the protocol. The DSMP report to NIH will also include, if applicable, the results of any hypothesis-testing data analysis conducted. External review. To ensure that the investigators employ appropriate data and safety monitoring strategies, we will have two external reviewers to monitor the study. [name] (assistant professor of psychiatry and human behavior at The Warren Alpert Medical School of Brown University and The Miriam Hospital) will be asked to review participant recruitment, retention, and statistical power. [name]. (a physician at Temple University) will be asked to review reports of adverse events in the surgicallytreated patients. In each case, reviewers will receive semi-annual summaries of our findings, following enrollment of the first participant. One of these two reports will coincide with the annual DSMP report. Reviewers will provide their evaluation and recommendations during regularly-scheduled telephone conference calls. Evidence of training in human subject research. All research personnel associated with this study will have completed the University of Pennsylvanias Collaborative Institutional Training Initiative (CITI) for patient oriented research, as well as HIPAA Compliance Training. Documentation of this training will be retained in the study regulatory binder.

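### The adverse-event reporting period ends at an 18-month visit that the study does not have, and the IRB reporting sentences do not form one rule

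*Combined protocol and SAP*

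**What the plan says.** The point concerns the Data and Safety Monitoring section of the combined protocol and SAP.

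**Reporting period.** "The study period during which adverse events must be reported is normally defined as the period from the initiation of any study procedures" and runs to the end of study treatment follow-up. The next sentence fixes that end: "the study treatment follow-up is defined as at the 18month study assessment visit".

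**Surveillance and duration, same section.** "Surveillance for SAEs and other relevant clinical events that may be associated with study participation will occur at 6, 12, and 24 months". The paragraph on expected events begins "Over the 24-month duration of the study, a number of medical events may be expected to occur".

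**Visit schedule elsewhere.** The Abstract says "Participants will complete four assessments over a two-year period, one at baseline (before surgery) and 6, 12, and 24 months after surgery". Administration of Surveys and/or Process and Subject recruitment both say "they will complete four study assessment visits over 24 months". Subject recruitment adds "Follow-up assessments will occur within an approximate 8-week window that includes 4 weeks on either side of the target date".

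**IRB reporting, in paraphrase.**
- The overview of how monitoring is performed sends every serious adverse event (SAE) to the IRB within 24 hours.
- The surveillance paragraph says that all adverse events are recorded, but that only those that are related, unexpected and serious are reported.
- The Monitoring and Reporting text sends any related and unexpected adverse event to the IRB within 10 days.
- The same text has SAEs notified to the investigators and study physician within 24 hours, then reported in a timely way as the monitoring plan (DSMP), the IRB and NIH require.
- It gives 24 hours for an unforeseen death that signals increased risk, and 3 days for all other deaths.
- The paragraph on expected events refers to unexpected events arising from participation, then says that the events go to the DSMP and not to the IRB.

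**The concern.** A reporting period needs an end that staff can identify. This one is tied to a visit that no participant will attend, and it falls before the last scheduled adverse-event questionnaire. The term study treatment follow-up gives no help, because the protocol states that surgery is not a study procedure.

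Staff at two sites apply this text, and summaries of adverse events go to NIH and to an external reviewer. The text leaves these questions open:
- When does the reporting period end?
- Does a non-serious event that is related and unexpected go to the IRB?
- Does an SAE that is unrelated or expected go to the IRB?
- Which time limit applies to deaths outside the unforeseen, increased-risk category?

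**Working it through.** The plan gives no derived figure to reproduce. The check compares passages and uses simple arithmetic.

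**1. Is there an 18-month visit?**
- *Visit count.* Baseline, 6, 12 and 24 months make 4 visits, equal to the stated four. There is no room for a fifth.
- *Payments (Subject compensation).* The plan pays 100 dollars at baseline, 50 dollars each "of participant payments for the 6and 12- month visits" and 100 dollars at 24 months: 100 + 50 + 50 + 100 = 300 dollars, the stated total. Nothing is left for an 18-month visit. The extra 25 dollars is for repeating measures before surgery.
- *Visit windows.* The window is 4 weeks either side of the target: 28 / 30.44 = 0.92 month. The 12-month visit can be no later than 12 + 0.92 = 12.9 months, and the 24-month visit no earlier than 24 − 0.92 = 23.1 months. Month 18 is about 5.1 months from either, so no scheduled visit can stand in for it.

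**2. What lies after the stated end?**
- Postoperative time: 24 − 18 = 6 of 24 months.
- Surveillance points at 6, 12 and 24 months: 1 of 3 falls after month 18.
- The period opens at the first study procedure, before surgery. So 6 of 24 describes postoperative time, not a share of the whole reporting period.

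**3. Do the IRB sentences agree?** Each event class is set against the sentences that reach it. The restrictive sentence is read as requiring all three attributes.

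| Event class | Reported to the IRB under | Limited or contradicted by |
|---|---|---|
| Non-serious, related and unexpected | 10-day rule | Restrictive sentence (not reported); expected-events paragraph, read literally (DSMP, not IRB) |
| Non-fatal SAE, related and unexpected | 24 hours (overview) | 10-day rule, which covers any such event; timely reporting, with no fixed limit |
| Non-fatal SAE, unrelated or expected | 24 hours (overview) | Restrictive sentence (not reported); timely reporting as others require |
| Unforeseen death signalling increased risk | 24 hours in both places | The two 24-hour statements agree |
| Any other death | 24 hours (overview, since a fatal event is an SAE by the section's own definition) | 3 days (Monitoring and Reporting); restrictive sentence if unrelated or expected |

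Only the fourth class has matching specific limits. For other deaths, reporting within 24 hours satisfies both limits, but the text still states two.

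**The case against.** The strongest reply is that the 18-month clause is one stray number among many consistent ones, and that staff could correct it from the schedule. Other text covers months 18 to 24:
- Adverse events are defined over the course of the study, and the study is called 24 months long.
- Surveillance is scheduled at 24 months, new findings are recorded at the end of the study, and monitoring runs in real time.
- The SAE, death and 10-day sentences carry no month-18 cut-off.

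All of this stands, and it limits the consequence. It does not supply an end to the period, because the only sentence that defines one names a visit that does not exist.

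The IRB points draw four further objections.
- *The restrictive sentence names no recipient and may list categories rather than require all three attributes.* This is fair. The all-three reading is the natural one in context, but the conflict depends on it. The authors should say which they mean.
- *The SAE sentence that defers to DSMP, IRB and NIH requirements may settle part of the question.* It may, by reference to sources not in the document. It does not remove the 24-hour limit in the overview.
- *The two limits for other deaths can both be met.* True, so the practical effect is small. They are still different limits.
- *The word unexpected under the expected-events heading is probably a slip, and the events sent only to the DSMP may be the expected ones just listed.* That is likely. As written, the paragraph conflicts with the 10-day rule, and correcting it is simple.

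**Conclusion.** The concern holds. The end of the adverse-event reporting period is wrong as written: it refers to a visit that the schedule, the visit count, the payments and the section's own surveillance plan all exclude. Nominally, 6 of 24 postoperative months and 1 of 3 surveillance points fall outside it.

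The IRB sentences also differ on their wording. The clearest cases are 24 hours against 3 days for other deaths, and the 10-day rule against the restrictive sentence. The second rests on reading that sentence as requiring all three attributes and as referring to IRB reporting.

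This is a gap in a written safety rule, not lost data. Sample size, power and the weight analyses are untouched. The conclusion assumes that no part of the application outside the text checked here schedules an 18-month visit. It takes no position on which IRB time limit is correct.

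**What to change.** Amend the Data and Safety Monitoring section as follows:
1. Delete the 18-month reference, and reconcile the end of the reporting period with the study's own final surveillance visit at 24 months.
2. Reconcile the IRB sentences so that each class has one route and one time limit: non-serious related and unexpected event, non-fatal SAE, unforeseen death, other death.
3. State whether related, unexpected and serious are required together, and to whom that sentence's reporting is directed.
4. Correct the expected-events paragraph to say whether the events sent to the DSMP and not to the IRB are expected or unexpected ones.

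The cost is a wording amendment. The 24-month questionnaire is already scheduled, so no new data collection is needed and no efficacy analysis changes.
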